Latest approval: December 21 2017

Title:

Para-cervical block prior to laparoscopic hysterectomy as an adjuvant treatment to reduce postoperative pain.

Project Summary:

Hysterectomy is one of the most common surgical procedures performed in the United States. Adequate analgesia and a faster recovery from surgery have become key factors that have taken the front stage in recent years. Increased use of minimally invasive techniques as well as the implementation of adjuvant treatments such as TAP-block are examples of strategies that have come into play in order to reduce postoperative pain scores and hasten recovery. We propose the use of a paracervical block with bupivacaine performed prior to a hysterectomy as a method to further reduce postoperative pain. This is a prospective, blinded randomized controlled trial in which patients that are scheduled to undergo a laparoscopic hysterectomy would be allocated to one of two groups: Paracervical block with local anesthetic (bupivacaine 0.5%), or placebo. After the patient is placed under anesthesia, 10 mL of 0.5% bupivacaine would be injected into the cervical stroma at 3 and 9 o'clock, which is standard technique for para-cervical block. The remainder of the procedure will then continue in a regular fashion. Alternatively, patients in the control group will be injected with 10 mL of normal saline. The surgeon would be blinded as to patient allocation. At the end of the case, pain will be assessed using a visual analogue scale with a range from 0 to 10 by one of the researchers who will also be blinded to the group. This will be done at 30 and 60 minutes after surgical stop time. Additional pain control in the PACU will be standardized to all patients. We will use T-Student tests to assure groups are homogenous to age, BMI, operating time, history of cesarean deliveries, and uterine weight. Chi-square and Ancova analysis will be utilized to determine if there is a significant difference in reported pain scores between groups. We will also stratify subjects based on uterine weight, history of cesarean delivery, additional procedures, etc. and determine if this has an effect on the reported pain scores.

Hypothesis:

Performing a para-cervical block with local anesthetic prior to a laparoscopic hysterectomy significantly reduces pain after the procedure.

Specific aims:

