Determine if infiltrating the cervical stroma with local anesthetic prior to performing a hysterectomy will reduce postoperative pain scores, and hence increase patient satisfaction.

Secondary aims:

Determine if there is a difference in baseline pain depending on additional procedures performed, and their response to the paracervical block.

Determine if there is a difference in response to paracervical block based on history of cesarean deliveries or uterine weight.

Background/Significance:

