intervention would be performed after the patient is under general anesthesia, prior to starting the surgery. Patients would be consented in the office or preoperative area (before receiving sedatives). As far as the intervention itself, it would consist of injecting 10 mL of 0.5% bupivacaine into the cervical stroma at 3 and 9 o'clock, which is standard technique for para-cervical block. The remainder of the procedure will then continue in a regular fashion. Alternatively, patients in the control group will be injected with 10 mL of normal saline. The surgeon would be blinded as to patient allocation. The formulations (saline or bupivacaine) will be previously prepared in a syringe in the operating room by a member of the research team prior to beginning the procedure. At the end of the case, pain will be assessed using a visual analogue scale with a range from 0 to 10 (Wong-Baker faces – appendix 1) by one of the researchers who will also be blinded to the group. This will be done at 30 and 60 minutes after surgical stop time. Additional pain control in the PACU will be standardized to all patients.

Study Subjects

Subjects will be selected based mainly on the fact they are undergoing a hysterectomy.

Inclusion criteria:

- Undergoing laparoscopic hysterectomy with or without salpingoophorectomy for benign indications
- Undergoing laparoscopic hysterectomy with robotic assistance with or without salpingoophorectomy for benign indications
- Between 18 and 60 years of age

Exclusion criteria:

- Intraoperative detection of malignancy
- Undergoing additional procedures at the time of surgery (except prophylactic McCall culdoplasty/uterosacral ligament suspension, excision of endometriosis, appendectomy, cystoscopy)
- Inability to perform paracervical block due to anatomic abnormalities (absent/flush cervix)
- Known allergy/sensitivity to bupivacaine
- Intraoperative bowel injury, bladder injury, ureter injury or major vessel injury that required repair.

Sample Size

Based on previous publications, it was determined that the expected mean pain score on postoperative day 0 after a TLH was 6 on the VAS, with a SD of 2. (10, 11) In order to detect

at least a 40% reduction in postoperative pain between groups, with a significance level of 5% and a power of 80%, a sample of 32 was required.

Data Collection

Data points to be collected are as follows:

- Age
- BMI
- Operating time
- History of cesarean deliveries

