- Preoperative indication for surgery (pain, prolapse, tumor, bleeding, etc)
- Procedures performed (if ovaries/tubes were removed, if robotic assistance was used, if any additional procedures that are exceptions from the exclusion criteria were performed).
- Specimen weight
- Uterine pathology
- Pain score at 30 minutes (see appendix 1 for Wong-Baker scale)
- Pain score at 60 minutes
- Number of days in the hospital (zero if discharged on same-day)

Data Handling

A master key will be generated during randomization. It will contain patient initials and medical record number, and an individual code. Only the primary investigator will have access to this master key.

A separate de-identified database using the individual code as index will be used for collection of all data points. The data that can be collected on the day of surgery (baseline characteristics, operating time, pain scores, etc) will be collected that day using a standardized form (appendix 2). This will later be transferred to the de-identified database. Using the master key, we will research pathology reports when available to complete final data points (uterine weight, histology, etc).

The data-collection sheets will be destroyed as soon as they are transferred into the de-identified database.

Data Analysis

We will use T-Student tests to assure groups are homogenous to age, BMI, operating time, history of cesarean deliveries, and uterine weight. ChiSquare and Ancova analysis will be utilized to determine if there is a significant difference in reported pain scores between groups. We will also stratify subjects based on uterine

weight, history of cesarean delivery, additional procedures, etc. and determine if this has an effect on the reported pain scores.

Time Frame

We expect to be able to consent and enroll at least two patients per week (average range of hysterectomy procedures per week from the surgeons that will participate is 5-10). We expect the data collection phase to span over 30 weeks approximately.

Strength/Innovation

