Patient satisfaction is a center point in today's healthcare. Faster recovery with less discomfort is not only standard of care, but may also translate into major economic advantages, such as less narcotic use and a decreased rate of postoperative admission. Using this technique as an adjuvant treatment for pain after laparoscopic hysterectomies has never been explored. There is data published for similar procedures, which demonstrates a clear benefit. If this study demonstrates significant improvement in pain scores, it has the potential to change standard of care for pain control during hysterectomy procedures.

Limitations

The main confounding factors are difference in operating style between surgeons and baseline surgical characteristics (large uteri that may require more dissection and tissue manipulation, etc.). To control for this we are only recruiting patients from 3 surgeons who have a similar operating technique. In addition to this, we are documenting operating time and specimen weight, which can be used to compare both groups and assure that they are homogenous to these potential confounders. Further analysis will also be made specifically stratifying the data based on these characteristics.

Risks

The risks of the procedure are minimal. Regarding possible adverse reactions to the local anesthetic, there is no additional risk given that this is already routinely administered during surgery. Patients will be screened to confirm they do not have a history of allergies to the medication. Possible reactions include hypotension, bradycardia, headaches, tremors, etc.

The paracervical block is routinely performed in the office setting before most invasive procedures involving the cervix, and risks are minimal, similar to those involving any subdermal injection. Possible risks include bleeding from injection site.

There is also the potential risk of accidental disclosure of the health information that will be collected.

Benefits

This study may find new methods of improving postoperative analgesia for patients undergoing minimally invasive hysterectomy procedures which may lead to less narcotic use, faster discharge from hospital, and greater satisfaction.

Costs

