12. ACOG Committee Opinion No. 444: choosing the route of hysterectomy for benign disease. *Obstet Gynecol.* 2009;114(5):1156-8.
13. Wong-Baker FACES Foundation (2016). Wong-Baker FACES® Pain Rating Scale. Retrieved 11/10/2016 with permission from <http://www.WongBakerFACES.org>.

Appendix 1

Wong-Baker FACES Pain Rating Scale (Used with permission)

©1983 Wong-Baker FACES Foundation. www.WongBakerFACES.org
 Used with permission. Originally published in Whaley & Wong's Nursing Care of Infants and Children. ©Elsevier Inc.

Appendix 2

Example of data collection form

Name:									Age:	MRN:	BMI:	
# of CDEL:	Indication(s) for surgery: 0 AUB 1 Pelvic pain 2 Prolapse 3 Fibroids 4 >4 Other: _____								Additional procedures performed: Oophorectomy Excision of endometriosis Vaginal vault suspension Minilap for tissue extraction Robotic Assistance YES NO			
Pain at 30 minutes: 0 1 2 3 4 5 6 7 8 9 10					Pain at 60 minutes: 0 1 2 3 4 5 6 7 8 9 10							
Days in hospital: 0 1 2 3 >3			Pathology: No abnormalities Adenomyosis Endometriosis Leiomyoma Other: _____					Spec weight: _____ grams	Operating time: _____ minutes

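### Two tests and two time points share the pain question, with no primary time, primary test, covariates or decision rule, so the 5% level is not ensured

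*Combined protocol and SAP*

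**What the plan says.** Specific aims sets the main question: "Determine if infiltrating the cervical stroma with local anesthetic prior to performing a hysterectomy will reduce postoperative pain scores". The subgroup questions are listed separately as secondary aims, so pain is plainly the main outcome.

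Study design fixes the assessments: "This will be done at 30 and 60 minutes after surgical stop time". The Appendix 2 form records each score as a whole number, for example "Pain at 30 minutes: 0 1 2 3 4 5 6 7 8 9 10".

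Data Analysis has one sentence on the comparison: "ChiSquare and Ancova analysis will be utilized to determine if there is a significant difference in reported pain scores between groups". The Project Summary repeats it without adding anything.

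Sample Size assumes that "the expected mean pain score on postoperative day 0 after a TLH was 6 on the VAS, with a SD of 2", and concludes, for a 40% reduction, "with a significance level of 5% and a power of 80%, a sample of 32 was required". It names no test and no assessment time.

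Strength/Innovation states what hangs on the result: "If this study demonstrates significant improvement in pain scores, it has the potential to change standard of care".

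**The concern.** Chi-square and ANCOVA are both assigned the same question, and each can be run at two times. That makes at least four results before any choice of covariates or of how to group a 0-10 score. The plan does not say which result decides, or whether one is enough.

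Two things are at stake. First, the actual type I error depends on the rule that is eventually applied, and it can lie above or below the 5% used for planning. Second, the results can conflict, with no rule for which one stands. If the choice of time, test, grouping or covariates is made after the scores have been compared by group, it can no longer be shown to be independent of the result. This is the test of the trial's only main hypothesis.

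**Working it through.** **1. Does any other section settle the choice?**

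- Time point: Sample Size refers to the day of surgery, which covers both scores. Specific aims and Strength/Innovation speak of pain scores in general.
- Test: Data Analysis and the Project Summary name both tests with equal standing.
- Covariates: age, BMI, operating time, cesarean history and uterine weight are listed for balance t-tests. Limitations uses operating time and specimen weight for group comparison and stratification. None is named as an ANCOVA covariate.
- Decision rule and chi-square grouping: not given anywhere.

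**2. The plan's own figure.** The difference is 0.40 × 6 = 2.4 points, with SD 2. The normal approximation gives n per group = 2(1.960 + 0.842)² × 2² / 2.4² = 10.9, so 11 per group and 22 in total. A t-test needs 12 per group, 24 in total. The stated 32 is not reproduced from the stated inputs. It is larger, and this point does not depend on it. Because 32 is not labelled as total or per group, results below are for 16 and for 32 per group. A two-sided t-test at one time then has power 0.907 and 0.997.

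**3. Bounds.** For two tests at 5% each, P(either) = 5% + 5% − P(both). If the two scores were independent, P(either) = 1 − 0.95² = 9.75%. If they were identical, it would be 5%. The answer lies between, according to the correlation.

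**4. Simulation of a comparison of means with no true difference.** From the plan: mean 6, SD 2, 0-10 scale. Assumed: 1:1 allocation, two-sided tests, bivariate normal scores rounded and clipped to 0-10, correlation between times 0.5 to 0.8. There were 20,000 trials per setting, so the simulation error near 9% is √(0.09 × 0.91 / 20,000) = 0.2 points.

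| Rule | 16 per group | 32 per group |
|---|---|---|
| One named time, or mean of the two | about 5% | about 5% |
| Either time significant | 8.0% to 9.2% | 7.8% to 9.2% |
| Both times significant | 0.9% to 2.2% | 1.0% to 2.0% |

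Widening the correlation to 0.3 to 0.9 gives 7.2% to 9.5% for either time. ANCOVA with three pre-listed covariates (8,000 trials per setting) gives 7.6% to 9.5% for either time and 0.5% to 2.2% for both.

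**5. Adding chi-square: false-positive rate if any of four tests may be claimed (illustration).** The grouping is assumed, since the plan gives none.

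| Form of chi-square | 16 per group | 32 per group |
|---|---|---|
| Full 0-10 scale | 12% to 13% | 12% to 14% |
| Cut at ≥4, ≥5, ≥6 or ≥7, uncorrected | 12% to 16% | 13% to 17% |
| Same cuts, continuity-corrected | 8% to 10% | 9% to 12% |

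**6. Power at one time for 6 vs 3.6.**

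| Test | 16 per group | 32 per group |
|---|---|---|
| Comparison of means | 90% | over 99% |
| Chi-square, full scale | 28% | 81% |
| Chi-square, cut ≥4 to ≥6 | 50% to 76% | 88% to 97% |
| Chi-square, cut ≥7 | 42% to 65% | 84% to 91% |

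Under this effect, the comparison of means and these forms of chi-square disagree on significance in 17% to 63% of trials at 16 per group and 3% to 19% at 32 per group.

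**The case against.** The strongest reply is that the plan nowhere says a single significant result is enough. Strength/Innovation speaks of scores in the plural, which could mean both times, and then the error rate is 1% to 2%. Strict rules are also affordable on the plan's own inputs. At 16 per group, requiring both times leaves 84% to 86% power for 6 vs 3.6, and testing each time at 2.5% leaves 84% to 88% for each. If the planned effect is real, the missing rule is unlikely to change the conclusion. All of this stands. It confines the harm mainly to a null or small effect, which is where a 5% level has to protect, and it shows that fixing a rule costs little. It does not supply the rule.

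The criticism of chi-square depends on its form. A linear-trend chi-square uses the order of the scores. At 16 per group it has 90% power and disagrees with the t-test in 0.3% of trials. That also stands: the power and disagreement figures above apply only to unordered and dichotomised tables. But the plan names no trend test, and the form is one more open choice.

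On covariates, the balance list sits just before the ANCOVA sentence, and Limitations names large uteri as a confounder. This is a visible candidate set, but it is assigned to another purpose. Operating time is known only after the block. Specimen weight reflects something present before the block but is measured afterwards, so a case can be made for it. Either way, the list has to be fixed in advance.

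**Conclusion.** The concern holds and must be fixed before any scores are compared by group. The absence of a primary time point, primary test, covariates and decision rule is a matter of reading and rests on no assumption. The size does rest on assumptions: the error rate is about 8% to 9% or about 1% to 2% according to whether either time suffices or both are needed, given the assumed correlation and two-sided tests. That contrast is the same whether 32 is the total or the number per group. The 8% to 17% range also needs a rule that any of four tests may win, plus a grouping the plan does not state, so it illustrates the exposure and is not an estimate of it. The power loss and the disagreement between tests are much smaller if 32 is per group.

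**What to change.** Revise Data Analysis, and the matching sentence in the Project Summary, to state:

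- **Primary endpoint:** one only, either pain at one stated time (30 or 60 minutes) or the mean of each patient's two scores.
- **Primary test:** one two-sided 5% comparison of means, reported with a 95% CI. Use either a t-test, or ANCOVA with covariates listed in advance from what is known before randomisation, for example age, BMI, number of cesarean deliveries or surgeon.
- **The other time-point results:** secondary, or the second time point tested only if the first is significant.
- **Chi-square:** not a primary test of pain scores. A categorised pain endpoint may stay as secondary if its cut-point is stated in advance.

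The cost is one paragraph and one sentence. No patients are added. No data are added unless surgeon is chosen as a covariate, which needs one more field on the Appendix 2 form. The sponsor gives up extra chances of a significant result. At 16 per group, three covariates that explain nothing lower power from 90% to 86% to 87%. If they jointly explain 20% of the variance (assumed), power is about 92% to 93%. All of these exceed the planned 80%.

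### The secondary aims ask whether response to the block differs by caesarean history, uterine weight or additional procedures, but no stated analysis compares the block effect across these strata

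*Combined protocol and SAP*

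**What the plan says.** The Secondary aims section sets two aims. The first is: "Determine if there is a difference in baseline pain depending on additional procedures performed, and their response to the paracervical block". The second is: "Determine if there is a difference in response to paracervical block based on history of cesarean deliveries or uterine weight". The second aim, and the latter half of the first, concern effect modification, that is, whether the bupivacaine-minus-saline difference varies with the factor.

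The Data Analysis section offers two relevant items. For the arms: "ChiSquare and Ancova analysis will be utilized to determine if there is a significant difference in reported pain scores between groups". No covariates or model terms are named. For the factors, subjects are stratified on uterine "weight, history of cesarean delivery, additional procedures, etc. and determine if this has an effect on the reported pain scores". The Project Summary says the same: "We will also stratify subjects based on uterine weight, history of cesarean delivery, additional procedures, etc". The Limitations section also promises stratified analyses, in a paragraph on confounding that names operating time and specimen weight as the recorded variables. No section gives an interaction term, a comparison of block effects between strata, or a cut-point for weight.

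**The concern.** The aims and the analysis address different quantities. A factor can raise pain equally in both arms, so that it has a clear effect on pain scores while the response to the block is the same for everyone. It can also change the response while leaving average pain almost unchanged. A test of the factor against pain cannot separate these cases.

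If stratifying means comparing arms within each stratum, the stratum-specific effects are available but the contrast between them is not. The tempting shortcut is to see which strata reach significance. With strata this small, a uniform effect could then be reported as working only in some women. What is at stake is what may be claimed about subgroups. The primary comparison is not affected.

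**Working it through.** **Inputs from the Sample Size section.** Control mean 6, SD 2, 40% reduction (0.40 × 6 = 2.4 points), 5% significance, and "with a significance level of 5% and a power of 80%, a sample of 32 was required". The text does not say whether 32 is the total or per arm, so both readings are shown.

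**Assumptions.** 1:1 allocation, two-sided test, normal scores, and a binary factor with equal strata unless stated. The plan gives no stratum prevalences.

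**The plan's own figure.** With 2.4 points, SD 2, two-sided 5% and 80% power, a t-test needs 12 per arm (24 in total), not 32. With 16 per arm power is 91%; with 32 per arm it is 99.7%. This mismatch is a separate matter and nothing below depends on it.

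**1. Literal reading: factor tested against pain, adjusted for arm.** SE = SD × √(4/N), which is 0.707 for N = 32 and 0.500 for N = 64.

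- *Same response, pain 2 points higher in both arms:* noncentrality 2/0.707 = 2.83 (29 df) gives 78%; 2/0.500 = 4.00 (61 df) gives 98%.
- *Different response, 1.2 versus 3.6 points:* the average stratum difference depends on control pain. If control pain in the high-response stratum is higher by c, the shift is c in the control arm and c − 2.4 in the block arm, averaging c − 1.2. It vanishes at c = 1.2. Simulation (100,000 trials) gives:

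| c | 0 | 0.6 | 1.2 | 1.8 | 2.4 |
|---|---|---|---|---|---|
| N = 32 | 34% | 11% | 4% | 11% | 34% |
| N = 64 | 62% | 19% | 4% | 19% | 62% |

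The test is often significant with no difference in response, and can miss a threefold difference almost entirely.

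**2. Within-stratum p-values, only if they are compared.** The power for 2.4 points is 29.9% with 4 per arm in a stratum, 60.8% with 8, 80.2% with 12, 90.7% with 16 and 98.3% with 24. The chance of exactly one significant stratum is p₁(1 − p₂) + p₂(1 − p₁).

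| Per arm in each stratum | Uniform 2.4 points | True 1.2 versus 3.6 |
|---|---|---|
| 8 / 8 (N = 32) | 2 × 0.608 × 0.392 = 48% | 75% |
| 12 / 4 (N = 32) | 0.802 × 0.701 + 0.299 × 0.198 = 62% | – |
| 16 / 16 (N = 64) | 2 × 0.907 × 0.093 = 17% | 62% |
| 24 / 8 (N = 64) | 0.983 × 0.392 + 0.608 × 0.017 = 40% | – |

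With equal strata, a real difference produces the pattern only 1.6 (N = 32) or 3.7 (N = 64) times as often as no difference.

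**3. Interaction test.** SE = 2 × √(2/n₁ + 2/n₂), where n₁ and n₂ are the numbers per arm in each stratum. True interaction 2.4 points:

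| n₁ / n₂ | SE | df | Power | 95% CI half-width |
|---|---|---|---|---|
| 8 / 8 | 1.414 | 28 | 37% | 2.9 |
| 12 / 4 | 1.633 | 28 | 29% | 3.3 |
| 16 / 16 | 1.000 | 60 | 66% | 2.0 |
| 24 / 8 | 1.155 | 60 | 53% | 2.3 |

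Under a uniform effect it is significant in 5%, so with equal strata a real difference is flagged 0.374/0.05 = 7.5 or 0.656/0.05 = 13 times as often.

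**The case against.** The strongest reply is that this is one loose sentence in a short protocol. It directly follows the arm comparison, so it may mean asking whether stratifying changes the between-arm result. The Secondary aims section already states the response question, and ANCOVA could carry an interaction. That is a fair reading, and it makes the gap one of under-specification rather than a wrong test. It still leaves the contrast between strata unstated, and that contrast is what the aims ask for.

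It is also fair that the harms are conditional. The plan does not say that within-stratum p-values will be compared, or that a factor's main effect will be reported as a difference in response. Stratum sizes and the 1.2-versus-3.6 scenario are assumed. With 32 in total, the interaction's CI half-width of 2.9 points exceeds the whole design effect. The gain is therefore mainly restraint in claims.

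Two points bear on the remedy. First, the design effect is a percentage. If control pain were 5 in one stratum and 7 in the other (assumed), a uniform 40% reduction would be 2.0 versus 2.8 points, an absolute interaction of 0.8. A linear model measures response in points, and the text should say so. Second, treating weight as continuous is not better in every case; the figures are given with the fix. Neither point removes the need to state the comparison.

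**Conclusion.** The concern holds. On neither reading does the stated analysis estimate or test a difference in block effect between strata, and the Limitations section does not supply it. Followed literally, the plan answers a different question from the one its response aims pose. The part of the first aim about baseline pain by additional procedure is served by the existing wording.

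The impact is low to moderate. It limits what can be said about subgroups and leaves the method, the weight cut-point and the grouping of procedures open until outcomes are known. The conclusion itself rests on the text alone. The percentages also depend on the assumed allocation, two-sided test, normality, strata and response scenarios. Over uniform effects of 1 to 3 points and strata from equal to 3:1, the one-significant-stratum pattern ranges from 26% to 62% (32 in total) or 3% to 60% (32 per arm).

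**What to change.** Keep the description of pain by additional procedure for the baseline-pain part of the first aim, and add to the Data Analysis section:

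> For each aim on response to the block, we will fit a linear model for pain score, separately at 30 and 60 minutes, with treatment, the factor and their interaction; response is the between-arm difference in points. Specimen weight will be continuous. Caesarean history will be yes/no, with the recorded number as a sensitivity analysis. The grouping of permitted additional procedures will be written down before outcome data are seen. Stratum-specific block effects may be shown. Interaction estimates with 95% CIs will be reported for all factors as exploratory, without multiplicity adjustment. No claim of differential response will be made from within-stratum p-values.

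**Cost.** This is mainly wording, because all three factors are already listed for collection. The Data Collection section asks "if any additional procedures that are exceptions from the exclusion criteria were performed", and the exclusion criteria permit "excision of endometriosis, appendectomy, cystoscopy" among others. The example form in Appendix 2, as it can be read here, shows no box for appendectomy or cystoscopy, so boxes may need adding.

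**Trade-offs.** Subgroup statements become more modest, given the low interaction power. Continuous weight avoids a cut-point but assumes linearity. The table gives simulated power, with weight assumed normal to lognormal (log-SD up to 0.8):

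| True pattern | Analysis | 32 in total | 32 per arm |
|---|---|---|---|
| Linear, 2.4 points over 2 SD of weight | Continuous | 25–33% | 51–62% |
| | Median split | 15–23% | 26–43% |
| Step of 2.4 points at the median | Continuous | 20–23% | 33–43% |
| | Median split | 28% | 55% |

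Three independent unadjusted tests carry a 1 − 0.95³ = 14% chance of at least one false positive. Six carry 1 − 0.95⁶ = 26%, and less if the two time points are correlated. This is why the results should be labelled exploratory.
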